2.3.1. Survey Completion

A respondent's data will be considered complete if that respondent has answered at least 1 discrete-choice question in the main DCE module. Respondents who do not meet this criterion cannot be included in the analysis because they provide no data on preferences.

2.3.2. Time to completion

The DCE survey is expected to take 20-30 minutes to complete; it includes several pages of reading materials and background questions in addition to the discrete-choice questions. We will assess the distribution of survey completion times and identify respondents that took too little time to complete the survey. We also will compare the time required to complete the survey between respondents who answered more or fewer comprehension questions correctly.

We will test the sensitivity of preference-estimate results to inclusion or exclusion of respondents who took less than 5 minutes to complete the survey since it is unlikely that an individual could read all the survey materials and give meaningful thought to their responses within that amount of time.

2.3.3. Response Non-Variance

The pacemaker alternatives in the choice questions are randomly assigned to first and second positions and there is no systematic relationship between the alternative placement and the attribute levels shown in each question. The probability that the preferred pacemaker alternative would appear in the same position for all 8 questions is less than 0.4%. For respondents answering 12 choice questions, the probability is just 0.02%. Therefore, we can infer that respondents who always select alternatives in the first or second positions are not attentive to the content of the choice questions. If response non-variance in the first or second position is observed for any respondent over the first 8 choice questions, their choice data will be excluded from the final analysis.

2.3.4. Attribute Dominance

In the DCE module, respondents choose among two pacemaker profiles in a series of choice questions. Some respondents may select the alternative with the better level of one attribute in all or most of these choice questions regardless of other attribute levels. When this response pattern is observed, it can indicate the respondent has a particularly strong preference for that attribute, and no combination of levels for the other attributes is sufficiently important to induce respondents to select an alternative with a less-preferred level of the dominant attribute. However, this pattern of dominated responses also could be evidence that a respondent simply made choices based on a single attribute to simplify the choice questions and thus avoid the effort of evaluating tradeoffs. It is not possible to definitively assess whether respondents with dominated response patterns expressed strong preferences for the dominant attribute or employed a simplifying heuristic; therefore, respondents who dominate on any attribute will be retained in the final sample.

We first will identify any respondents who selected the alternative with the better level of one attribute in all of the first 8 choice questions that have no overlapping levels, indicating dominated preferences for that attribute. We will report the numbers and percentages of respondents who dominated on each attribute. If more than 15% of the sample is observed to dominate on a single attribute, we will assess the impact of attribute dominance on the preference model estimates during the exploratory analysis phase (see Section 2.4). We also will test whether time spent completing the survey and responses in the background and treatment characteristics sections of the survey differed significantly between respondents who dominated and those who did not dominate. This analysis will be completed as part of the assessment of the background characteristics in latent-class analysis described in Section 2.4.4.

2.4. Specifying a Benefit-Risk Tradeoff Preference Model

Predetermining the specification of a regression model for analyzing choice data can lead to biased models, result in unnecessarily wide confidence intervals, and ultimately, result in missed opportunities to fully understand patients' preference patterns. To avoid these problems, this section outlines the initial analyses that will be conducted to evaluate relationships between respondents' choices and attribute levels, and it describes several potential exploratory analyses that will be conducted.

2.4.1. Initial Analyses

[figure not shown]
We will begin analyzing the choice data using a conditional logit model with effect-coded variables for all levels of each attribute. This model specification imposes the fewest assumptions regarding functional forms across preference weights within the study attribute levels but imposes simplifying assumptions on error terms.

Conditional-logit models run very quickly and often produce results similar to more complex models. We will use this initial model to identify any attributes and levels that require further investigation. For example, findings such as relationships between the estimated preference weights and levels within an attribute, interactions between attributes, or disordered preference weights (where clinically inferior levels are preferred over superior clinical levels) would require further exploratory analysis.

[figure not shown]
2.4.2. Scope Test

As explained in Section 1.1.2, we embedded a scope test to evaluate whether respondents are sensitive to the actual risk levels shown. Respondents assigned to the low-risk arm will see maximum risk levels of 10% for both the infection risk and complication risk attributes. Respondents assigned to the high-risk arm will see maximum risk levels of 20% for both risk attributes. If respondents systematically recode the risk levels qualitatively (for example, as low, medium, and high), the scope test would show that preference estimates are not sensitive to the overall risk range (i.e., the relative weight for the 10% level in the low-risk arm is not different than the relative weight for the 20% risk level in the high-risk arm). Because the other two levels in the experimental design overlap between arms, we can also assess whether the overall preference for the 1% and 5% risk levels are influenced by the maximum risk levels that respondents evaluate.

2.4.3. Subgroup Analyses

² Centers for Disease Control and Prevention. Defining adult overweight and obesity. <https://www.cdc.gov/obesity/adult/defining.html>. Accessed August 27, 2021.

- [REDACTED]
- [REDACTED]
- [REDACTED]

2.4.5. Exploratory Preference Model

A series of horizontal black bars of varying lengths, creating a visual effect similar to a film strip or a series of frames. The bars are arranged vertically, with some being significantly longer than others, suggesting a sequence of events or frames.

A series of seven horizontal black bars of varying lengths, decreasing in size from top to bottom. The bars are evenly spaced and extend across the width of the frame.

2.5. Equivalence Values

Preference-weight estimates from the final random-parameters logit model will be used to compute equivalence values in terms of risk-equivalent values and time-equivalent values as a means to compare the relative importance of preferred device features for the full cohort.

We will compute the maximum-acceptable risk (MAR) of infection and the MAR of complications that respondents would accept in exchange for their preferred pacemaker type, no discomfort, a device with longer battery life, and a device with more time since regulatory approval. We will compute MARs using the following steps:

The same approach described above can be used to estimate time equivalents where preference utility gains (i.e. log odds preference weights) for preferred pacemaker features are offset using equivalent reductions in preference utility gains for time attributes (i.e. reductions in years of battery life and smaller/larger number of years since regulatory approval). For example, this approach can be used to determine the maximum reduction in battery life that the average respondent would accept to avoid pacemaker-associated discomfort.

2.6. Predicted Choice Probabilities

Preference-weight estimates from the final random-parameters logit model will be used to compute (or simulate) the probability that the average respondent would choose a pacemaker profile defined by study attribute levels, compared with a profile with different study attribute levels.

Table 3. Pacemaker Profiles for Predicted Choice Probabilities

2.7. Ranking Exercise

To evaluate respondents' level of concern about device type-specific features, we will first report the numbers and percentages indicating which type of insertion procedure, the presence or absence of leads, and the location of the pacemaker is of greater concern. We also will report the number and percentage of respondents indicating that all three features associated with a transvenous pacemaker (i.e. insertion through chest, pacemaker with leads and pacemaker

placed under the skin on the chest) were of greater concern. We also will report the number and percentage of respondents indicating that all three features associated with a leadless pacemaker (i.e. insertion through a catheter, pacemaker without leads and pacemaker placed inside the heart) were of greater concern.

We then will compute the mean rank order for each device feature evaluated. For device features pertaining to procedure type, presence of leads and pacemaker location, the rank assigned to the type selected will be included in the mean estimate. When the feature type was not selected in the preceding question, the rank will be treated as missing. Therefore, the mean ranks will be conditional on the feature having been selected (or not available for selection- limited activity for 2 weeks, no scar on chest, no lump on chest).

We also will report the percentage of times that each device feature (without regard to which procedure type, presence of leads and pacemaker location was chosen) was chosen as the most concerning feature. Then, conditional on the number one ranking, we will report the percentage of times each type of device feature was chosen (e.g. when procedure type was the most concerning feature, the percentage of the time it represented insertion through the chest wall versus insertion through a catheter in the groin).

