5. OBJECTIVES

5.1. Primary

The primary objective of the study is to quantify patient preferences for pacemaker device features. This includes estimates of the following:

- The conditional relative importance of device features included in the DCE
- Maximum percentage-point increases in the acceptable risk of complications or infection for an improvement in another attribute (for example: to get a preferred device type, to avoid discomfort, or to have a device with longer battery life)

- Other value equivalents (for example: What patients will give up in terms of years of battery life to move from a less-preferred device type to a more-preferred device type).
- Predicted choice probabilities for product profiles relative to specified comparators (i.e. the likelihood that an average respondent in the sample would choose a device profile with specific features, compared with a profile with different features)
- Mean ranking of select device features not included in the DCE (i.e. insertion procedure, visible lump of the generator, and scar on chest or groin)

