11.3. Study Endpoints

Study endpoints will include a set of log-odds preference weights for all attribute levels included in the DCE. From these preference weights, the following endpoints will also be calculated:

- The conditional relative importance of device features included in the DCE
- Percentage-point increases in the maximum-acceptable risk (MAR) of complications or infection for an improvement in another attribute (for example: to get a preferred device type, to avoid discomfort, or a have a device with longer battery life)
- Other value equivalents (for example: What patients will give up in terms of years of battery life to move from a less-preferred device type to a more-preferred device type)
- Predicted choice probabilities for product profiles relative to specified comparators (i.e. the likelihood that an average respondent in the sample would choose a device profile with specific features, compared with a profile with different features)

Mean ranking of select device features not included in the DCE (i.e. insertion procedure, visible lump of the generator, and scar on chest or groin) will be estimated.

12. Analysis

Discrete-choice experiments generate complex cross-section/time-series choice data for each respondent. These data include a dichotomous dependent variable and are analyzed using advanced statistical methods. The basis for the analysis is the model specification assumed when generating the experimental design prior to survey implementation. That specification considers a categorical main-effects model for all study attributes. However, the specification assumed in the experimental design takes into account only statistical considerations. The statistical analysis of choices will provide a measure of the impact of changes in the attribute levels on the likelihood that treatments are selected by respondents, also referred to as attribute-level preference weights.

Respondents' reactions to the stimuli in DCE questions generally involve complex decision processes, and the final model specification must account for the pattern of choices as observed in the data set. The Statistical Analysis Plan from the DCRI [REDACTED] lays out the initial analyses that will be conducted to assess the quality of the data and describes exploratory analytic strategies that will inform the final model specification.

The design and study specifications have been developed to support a robust analysis and reporting that will include the following:

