1.2. Ranking Question

To gain insights about device features that are inextricably linked to a specific type of pacemaker and thereby not amenable to inclusion in a DCE, a ranking exercise was designed to elicit information on participants' relative concern for these device features. These features include the insertion procedure, where the device is implanted/resides in the body, the need for leads, whether the device is externally visible, and duration of activity restrictions after the device is implanted (Table 2).

In a ranking exercise, it is important that all features included in the exercise are either positive or negative. Because the options pertaining to the insertion procedure, presence of leads and location are not clearly positive or negative, survey respondents are first asked to indicate which specific aspect of a pacemaker attribute is of greater concern for these three features (see first three rows of Table 2 below). For example, with regard to leads, respondents could choose "having a pacemaker without leads" or "having a pacemaker with leads", as shown in Table 2. The chosen feature of greater concern is then transferred to the ranking exercise so that all features shown in the ranking exercise represent negative aspects of pacemakers from the patient perspective.

Table 2. Items in the Ranking Exercise

Insertion procedure

• Pacemaker inserted through cut in skin on the chest• Pacemaker inserted using tube through the groin
Leads

• Having a pacemaker with leads• Having a pacemaker without leads
Pacemaker location

• Having a pacemaker placed under the skin on the chest• Having a pacemaker attached to the walls inside the heart
No heavy lifting is allowed for 6 weeks (versus limited activity for 2 weeks)
Scar on chest (versus no scar)
Lump on chest (versus no lump)

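### SAP 2.7 makes the mean ranks for insertion, leads and location conditional on selection, so rows are not comparable, and the protocol's feature-level mean rank is not explicitly specified

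*SAP*

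**What the plan says.** Protocol 5.1 lists under the primary objective: "Mean ranking of select device features not included in the DCE (i.e. insertion procedure, visible lump of the generator". Protocol 11.3 repeats this among the endpoints. In both places the insertion procedure is one feature, not two options.

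Protocol Table 3 and SAP Table 2 give the ranking items. Three features (insertion, leads, location) have two sides each. Respondents first say which side worries them more, and SAP 1.2 continues: "The chosen feature of greater concern is then transferred to the ranking exercise". The other three items are fixed: the lifting restriction, the chest scar and the chest lump. Each respondent therefore ranks six items.

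SAP 2.7 sets out the analysis in this order:

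- The number and percentage choosing each side of the three two-sided features.
- Mean ranks: "We then will compute the mean rank order for each device feature evaluated". For the two-sided features, "the rank assigned to the type selected will be included in the mean estimate". Then "When the feature type was not selected in the preceding question, the rank will be treated as missing", so that "the mean ranks will be conditional on the feature having been selected".
- The percentage of times each feature was ranked most concerning, pooled over its two sides, and then the split of those first places by side.

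**The concern.** If an unselected side is set to missing and the mean is conditional on selection, each side of a two-sided feature gets its own mean over only those who chose it. The fixed items are averaged over everyone who ranked. The results would then be up to nine means with different denominators and different groups of people. Whether a respondent counts towards a side depends on the concern being measured, so the order of the nine means need not be the sample's order of concern.

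The protocol's quantity is a mean rank per feature. A feature-level mean over both sides would have no missing ranks (given complete rankings) and nothing to condition on, so the last two sentences of the mean-rank rule point away from it. Protocol section 4 says the results are to inform technology development, support regulatory review and potentially support labeling. The sides of the two-sided features divide along transvenous versus leadless lines. A small, intense minority could therefore make a feature of one device type look like a leading concern of the whole sample.

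**Working it through.** **Inputs.** From the documents: six ranked items per respondent, two sides for three of them, and a minimum sample of 300 (Protocol section 8). The documents give no expected ranks, selection shares or precision for this exercise, so there is no figure to reproduce. All shares and mean ranks below are assumptions. Rank 1 is the most concerning.

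**Step 1: link between the two kinds of mean.** If a share p of those who ranked chose side A:

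feature mean = p × (mean rank of A among its choosers) + (1 − p) × (mean rank of B among its choosers).

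With assumed conditional means of 1.5 (A) and 3.5 (B) and N = 300:

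| p | n choosing A | Row for A | Feature mean |
|---|---|---|---|
| 5% | 15 | 1.5 | 0.05×1.5 + 0.95×3.5 = 3.40 |
| 10% | 30 | 1.5 | 0.10×1.5 + 0.90×3.5 = 3.30 |
| 20% | 60 | 1.5 | 0.20×1.5 + 0.80×3.5 = 3.10 |
| 50% | 150 | 1.5 | 0.50×1.5 + 0.50×3.5 = 2.50 |

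The option row is 1.5 throughout and carries no information on how many people it represents.

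**Step 2: common base.** With complete rankings each respondent's ranks sum to 1+2+3+4+5+6 = 21, so the six feature means sum to 21 and average 21/6 = 3.5. The nine conditional means have no such constraint.

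**Step 3: can the order reverse?** A simulation used 300 respondents, 2,000 runs per setting and random (Gumbel) utilities. The mean concern was set at 0.3 for insertion and location, 0 for the three fixed items and −0.5 for leads among the majority. A minority chose the without-leads side, with concern −0.5 (same as the majority), 0.3 (moderate) or 1.5 (strong).

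| Minority share | Minority concern | Option has best of nine means | Its conditional mean | Leads feature mean | Leads: average place of six |
|---|---|---|---|---|---|
| 5% | same | 0.2% of runs | 4.25 | 4.25 | 6.0 |
| 5% | moderate | 26% | 3.25 | 4.19 | 6.0 |
| 5% | strong | 99% | 2.02 | 4.13 | 6.0 |
| 10% | same | 0.05% | 4.24 | 4.24 | 6.0 |
| 10% | moderate | 17% | 3.28 | 4.15 | 6.0 |
| 10% | strong | 100% | 2.01 | 4.02 | 6.0 |
| 20% | same | 0% | 4.24 | 4.25 | 6.0 |
| 20% | moderate | 12% | 3.28 | 4.06 | 6.0 |
| 20% | strong | 100% | 2.01 | 3.80 | 5.7 |

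The leads feature itself never came first. Its low place follows from the assumed weak concern of the majority. In the moderate setting the minority's concern equals that set for insertion and location, so its first places there largely reflect the noise of a small row.

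One run at an expected 10% minority with strong concern shows the mechanism. Without leads averaged 1.875 (n = 32) and with leads 4.179 (n = 268). The feature mean was (32×1.875 + 268×4.179)/300 = (60 + 1,120)/300 = 3.93, the last of the six. The six feature means summed to 21.0; the nine conditional means summed to 29.3.

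**Step 4: precision.** If all six ranks were equally likely, the SD would be √(35/12) = 1.71, and the 95% half-width 1.96 × 1.71/√n would be 0.86 at n = 15, 0.61 at n = 30 and 0.19 at n = 300. This is a reference for a mean near 3.5 only. On a 1 to 6 scale with mean m, the SD cannot exceed √((m − 1)(6 − m)), which is √(0.5×4.5) = 1.5 at a mean of 1.5. A row with a very low mean is therefore less noisy than these half-widths suggest, but its n still differs from that of the fixed items.

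**The case against.** A reader might infer that the SAP never produces the protocol's feature-level mean. The text does not support that. The sentence promising a mean rank for each feature, with the rank of the selected type entering the mean, can be read as one pooled mean per feature. Only the next two sentences favour option-level means. The pooled mean also follows by the Step 1 formula from the conditional means and selection counts, provided those counts refer to the people who ranked. The accurate statement is that it is not explicitly specified.

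A reader might also infer that a rare option will head the results. That needs strong concern among its choosers, and no document gives such a figure. The SAP does not specify a single ordered nine-row table either.

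The SAP has real safeguards. It reports how many chose each side. It also reports, pooled over sides, how often each feature was ranked first, with the split by side; multiplying those two gives the share of all respondents who both chose a side and ranked it first. A careful reader could see that a striking row rests on few people. This stands as partial protection, but a first-place share is not a mean rank and ignores ranks two to six.

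The missing ranks are structural. An unselected side is never ranked, so nothing is lost, and the conditional mean is not biased for its own stated target. The fault lies only in comparing rows. The option-level means also have their own use: a pooled leads mean combines opposite worries and cannot show which device type causes them. That is a good reason to keep them in view.

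Finally, mean ranking is one of five items under the primary objective and is purely descriptive.

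**Conclusion.** The point holds as a matter of comparability and specification. On the natural reading of SAP 2.7, the means for the sides of insertion, leads and location rest on different self-selected subsets. They are not comparable with each other or with the three fixed items. The feature-level mean rank listed in Protocol 5.1 and 11.3 is left to be derived, and two analysts could produce different tables from the same text.

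The size cannot be fixed from the documents. Under the assumed settings, a side chosen by 5% to 20% had the best of the nine means in 99% to 100% of runs with strong minority concern, in 12% to 26% with moderate concern, and in 0.2% or fewer with concern equal to the majority's. No sample-size, power or error-rate figure is affected. This is a free improvement, not a defect that threatens the study.

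There are two separate wording mismatches. The protocol endpoint includes "visible lump of the generator, and scar on chest or groin", but the only scar item ranked is on the chest. The SAP's parenthetical list of fixed items names the comparator sides (the shorter activity limit, no scar, no lump) in place of the items ranked. Neither adds to the main point.

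**What to change.** Add to SAP 2.7 a mean rank for each of the six features over all respondents who ranked, using the rank of whichever side was shown. State that this table is the one for comparing features. With complete rankings the six means average 3.5, which also serves as a programming check.

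Keep the option-level means alongside it, labelled as conditional on selection, with n printed for each row. Leave the planned selection percentages and first-rank percentages as they are.

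As a wording correction only, align the protocol's scar wording and the SAP's parenthetical list with the items actually ranked.

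The cost is a few lines of text and one extra table from data already planned for collection.
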